9.0 Vulnerable Populations*

cementation

If the research involves special populations that are considered vulnerable, describe the safeguards included to protect their rights and welfare.

Page 17 of 49

NOTE: You should refer to the appropriate checklists, referenced below, to ensure you have provided adequate detail regarding safeguards and protections. You do not, however, need to provide these checklists to the IRB.

9.1 For research that involves **pregnant women**, safeguards include: NOTE CHECKLIST: Pregnant Women (HRP-412)

Response:

- N/A: This research does not involve pregnant women.

 N/A: This research does not involve pregnant women.
- 9.2 For research that involves **neonates of uncertain viability or non-viable neonates,** safeguards include:
 NOTE CHECKLISTS: Non-Viable Neonates (HRP-413), or Neonates of Uncertain

NOTE CHECKLISTS: Non-Viable Neonates (HRP-413), or Neonates of Uncertain Viability (HRP-414)

Response:

- N/A: This research does not involve non-viable neonates or neonates of uncertain viability.
- 9.3 For research that involves **prisoners**, safeguards include: NOTE CHECKLIST: Prisoners (HRP-415)

Response:

- 9.4 For research that involves persons who have not attained the legal age for consent to treatments or procedures involved in the research ("children"), safeguards include:

NOTE CHECKLIST: Children (HRP-416)

Response:

- □ N/A: This research does not involve persons who have not attained the legal age for consent to treatments or procedures ("children").
- 9.5 For research that involves **cognitively impaired adults**, safeguards include: NOTE CHECKLIST: Cognitively Impaired Adults (HRP-417)

Response:

Adequate provisions will be made for soliciting the permission of parents or guardians.

Adequate provisions will be made for soliciting the assent of the children.

No greater than minimal risk to children will be present.

The research presents the prospect of direct benefit to the individual subject.

Permission is to be obtained from one parent or guardian

- N/A: This research does not involve cognitively impaired adults.
- 9.6 Consider if other specifically targeted populations such as students, employees of a specific firm, or educationally or economically disadvantaged persons are vulnerable. Provide information regarding their safeguards and protections, including safeguards to eliminate coercion or undue influence.

Response: We are not specifically targeting a vulnerable group.

10.0 Eligibility Screening*

- 10.1 Describe **screening procedures** for determining subjects' eligibility. Screening refers to determining if prospective participants meet inclusion and exclusion criteria.
 - Include all relevant screening documents with your submission (e.g. screening protocol, script, questionnaire).

Response:

Patients will be screened by their assigned residents according to the protocols set up in the UB Orthodontic Clinic. Each new patient is screened using a specific form supplied by the UB Orthodontic clinic regardless of whether they participate in research or not (I have included a copy of this form with my submission). One research examiner (AN) will review all patient screening forms to determine if the patient meets all necessary inclusion criteria. Once orthodontic records have been taken on the patient by the treating resident, the examiner (AN) will review the records taken (photos, x-rays, digital casts) to confirm that the patient meets all the inclusion criteria in order to participate.

 \square N/A: There is no screening as part of this protocol.

11.0 Recruitment Methods

- N/A: This is a records review only, and subjects will not be recruited. NOTE: If you select this option, please make sure that all records review procedures and inclusion/exclusion screening are adequately described in other sections.
- 11.1 Describe when, where, and how potential subjects will be recruited.

NOTE: Recruitment refers to how you are identifying potential participants and introducing them to the study. Include specific methods you will use (e.g. searching charts for specific ICD code numbers, Research Participant Groups, posted advertisements, etc.).

Response:

Subject requirement for the study will be utilizing the current advertising methods in place at the University at Buffalo School of Dental Medicine's Orthodontic Clinic. Nothing new will be mentioned regarding the study in the current advertising methods. New patient screenings will be utilized for study screening purposes and recruitment. If patients meet the necessary inclusion criteria, they

will be contacted by the research examiner and recruited for the study. All necessary information, consent forms and waivers will be provided to the subject and appropriate guardian.

11.2 Describe how you will protect the privacy interests of prospective subjects during the recruitment process.

NOTE: Privacy refers to an individual's right to control access to him or herself.

Response:

Prospective subjects will be invited to participate in the current study in a separate room away from other patients/subjects. All subject records, which include health and personal information, will be kept strictly confidential abiding by privacy laws and our own clinic regulations. These records will be encrypted and kept on a password protected computer in the Orthodontic clinic at the University at Buffalo School of Dental Medicine. The subject will have full access to their records. There is restricted access to all patients/subjects utilizing the AXIUM patient management software in place in our clinics. Only treating residents are allowed to view patient records as well as faculty in the Orthodontics department at the University at Buffalo School of Dental Medicine. Subject records and data will not be shared or viewed by anyone other than the examiner and supervising faculty.

11.3 Identify any materials that will be used to recruit subjects.

NOTE: Examples include scripts for telephone calls, in person announcements / presentations, email invitations.

For advertisements, include the final copy of printed advertisements with your submission. When advertisements are taped for broadcast, attach the final audio/video tape. NOTE: You may submit the wording of the advertisement prior to taping to ensure there will be no IRB-required revisions, provided the IRB also reviews and approves the final version.

Response:

N/A

12.0 Procedures Involved*

12.1 Provide a description of **all research procedures or activities** being performed and when they are performed once a subject is screened and determined to be eligible. Provide as much detail as possible.

NOTE: This should serve as a blueprint for your study and include enough detail so that another investigator could pick up your protocol and replicate the research. For studies that have multiple or complex visits or procedures, consider the addition of a schedule of events table in in your response.

Response:

Subjects will be recruited patients from the Orthodontics Clinic at the University at Buffalo School of Dental medicine who are undergoing comprehensive orthodontic treatment. Patients a unilateral or bilateral ½ cusp to full-cusp Class II molar relationship with mild-moderate crowding will qualify for participation. At the orthodontic consult appointment, eligible patients will receive information on the study and will be asked to participate. A randomization protocol will be followed in order to assign subjects to 1 of 2 study groups for Class II correction (CMA v. In-office fabricated Class II correction appliance) once the subject and parents have agreed to participate in the study and have filled out consent forms. Initial records will be taken at T0 (intraoral photographs, 3D scan, radiographs) before starting orthodontic treatment.

Models of subjects assigned to the in the in-office fabricated appliance group will be 3D printed, and one operator (AN) will fabricate custom devices for each subject. The buccal surface of the maxillary first molar will be etched for 12s using 35% phosphoric acid, rinsed, dried, and Assure Plus bonding agent will then be applied to the buccal surface of the maxillary first molar, and light cured for 10 s using an LED curing light. A pre-pasted 0.022 Slot MBT second molar minitube that has been modified to have a 2 mm tube length will be placed in the center of the buccal surface of the maxillary first molar and light cured for 40 s. A 0.016x0.022 stainless-steel wire will be roughly sectioned to be longer than the distance from the maxillary first molar to the maxillary canine for ease of placement. Once the wire has been placed through the buccal tube of the molar bracket, it will be marked and a bayonet bend will be placed mesial to the molar tube. A slight curve will be bent into the wire to span the premolars, so that the wire is able to passively rest on the buccal surface of the maxillary canine. The wire will then be used to position the canine bracket, so that the wire rests passively in both the canine and molar brackets. The maxillary canine will be prepared using phosphoric acid etch and assure plus in the same fashion as the molar bracket. A 0.018 MBT maxillary canine bracket will be placed and cured using the stainless-steel wire as a template to ensure passive placement. Once both brackets are placed, the wire will be cut so that a small section of wire remains mesial to the maxillary canine and distal to the maxillary first molar. The wire will then be cinched mesial to the maxillary canine tie-wing. The wire will also be cinched distal to the maxillary first molar, with 2-3 mm of excess wire distal to the maxillary first molar to ensure that the molar can rotate during treatment, if needed. The distance from the mesial opening in the buccal tube of the maxillary first molar to the most distal portion of the canine bracket will be measured, and an closed-coil stainless-steel spring will be sectioned to measure the span from the distal tie-wing of the maxillary canine to the mesial portion of the maxillary molar tube. The wire will be placed into the brackets with the closed-coil spring spanning the molar and canine, and a stainless-steel tie will be used to secure the wire into the canine bracket. The fabricated device will then be removed from the model and the excess cement on the molar and canine pad will be carefully removed prior to cementation in the patient's mouth.

For the CMA group Orthocad software will be used by one operator (AN) in order to measure the distance from the center of the buccal surface of the first molar to

the center of the facial surface of the canine (in mm). This measurement will be used to determine the proper size CMA device needed for the study.

Prior to the bonding appointment, digital cases of the mandibular arches of all subjects will be 3D printed, and essix retainers with 2 mm thickness will be fabricated to include an opening on the buccal surfaces of the mandibular first molars for placement of a button to anchor the Class II elastics during treatment.

At the bonding appointment, for both study groups, proper isolation methods will be placed according to the treating resident's preference. Maxillary first molars and canines will be etched using 35% phosphoric acid for 12 s, rinsed, and air thinned using an air water syringe. Assure plus bonding agent will be placed on the molar and canine buccal surfaces, air thinned, and light cured for 10 s. Packable composite will be placed on the molar and canine pads (CMA group) or the maxillary first molar tube and canine bracket (in-office appliance group). The molar pad (for the CMA group) and the first molar bracket (for in-office appliance group) will be positioned onto the center of the buccal surface of the maxillary first molar, and once it has been properly positioned, the canine pad (CMA group) or canine bracket (in-office appliance group) will be placed passively. Excess cement will be removed, and each pad/tube/bracket will be light cured using an LED curing light for 40 s. The mandibular essix retainer will then be placed and adjusted according to patient comfort level. Once the patient is comfortable with the essix retainer, it will be used as a template to mark the buccal surfaces of the mandibular first molars for placement of the buttons. The mandibular first molars will be etched using 35% phosphoric acid for 12 s, rinsed, and air thinned using an air water syringe. Assure plus bonding agent will be placed on the molar and canine buccal surfaces, air thinned and light cured for 10 s. Packable composite will be placed on the pad of the orthodontic buttons, and the buttons will be placed and excess cement will be removed. The buttons will be light cured for 20 s each.

Isolation will then be removed and the patient will be instructed to wear the essix retainer 24 hours a day and to only take it out to eat and when completing hygiene methods. The patient will be given Force 1 Class II elastics (1/4, 6 oz) and will be instructed on how to place them from either the hook on the canine pad (CMA group) or the hook on the canine bracket (in-office appliance group) to the button on the mandibular first molars. The patient will be instructed to wear the elastics 24 hours a day and to only remove them when eating and completing hygiene methods, and to change elastics daily.

The patient will be seen 1 month later and will be given Force 2 Class II elastics (3/16, 8 oz) and will be instructed to wear them using the same protocol for the remainder of their class II correction. The patient will be evaluated each month until a Class I molar and canine relationship has been obtained.

Once a Class I molar and canine relationship has been obtained, The CMA or in office appliance will be removed, and an intraoral scan and lateral cephalometric radiograph will be taken immediately after removal of the appliance(s) (T1). The

total duration (in months) of Class II correction, starting at the bonding appointment and ending at the T1 appointment will be recorded for each subject.

Superimposition & Data Analysis

Once T0 and T1 records are obtained, lateral cephalometric tracing and measurements will be completed and recorded by one operator (AN). Superimpositions will be constructed using T0 and T1 lateral cephalometric tracings. Initial cephalometric measurement (T0) will be subtracted from final cephalometric measurements (T1) for each value (Please see table in section 12.2 for a complete list of lateral cephalometric measurements and their descriptions).

Intraoral scan data will be collected with an iTero Element 3D Scanner. Digital models will be superimposed using the Best fit method described in a study conducted by Grünheid and Larson. Maxillary model superimpositions will be used to address the difference in maxillary first molar and canine rotational positions before versus after Class II correction (°). Mean values for all measurements (lateral cephalometric and digital model superimposition) will be calculated for each treatment group and statistical analyses will be ran using he Statistical Package for the Social Sciences (SPSS) to compare means.

Intra-examiner reliability will be addressed by randomly selecting 5 lateral cephalograms 2 weeks after initial measurements were performed and having the same operator (AN) repeat the landmarking, superimpositions and measurements. The same operator will also repeat measurements on 5 casts 2 weeks after measurements are conducted for the maxillary first molar and canine rotational measurements. Intra-class correlation coefficients will be calculated in order to determine intra-examiner reliability based on the first and second measurements (P < 0.05).

12.2 Describe what data will be collected.

NOTE: For studies with multiple data collection points or long-term follow up, consider the addition of a schedule or table in your response.

Response:

Patient Age

Total treatment time (in months) starting from the initial bonding appointment to T1 appointment

3D position of the maxillary molar and maxillary canine (using digital models) at T0 and T1

Lateral cephalometric values (listed below) at T0 and T1

Page 23 of 49

Cephalometric Dentoalveolar Measurements

X-Axis	SN minus 7 degrees	
Y-Axis	Perpendicular line to the X-axis drawn through the S point	
U6-Y (mm)	Linear distance of the maxillary first molar to the Y plane	
L6-Y (mm)	Linear distance of the mandibular first molar to the Y plane	
IMPA (°)	Incisor mandibular plane angle	
L1-Y (mm)	Linear distance of the mandibular central incisor to the Y plane	
L1-NB (mm)	Linear distance of the mandibular incisor to a vertical line drawn through Nasion and Point B	
L1-NB (°)	Angle between the mandibular incisor and a vertical line drawn through Nasion and Point B	
L1-APo (mm)	Linear distance of the mandibular incisor to a vertical line drawn through Point A and Pogonion	
U6-PP (°)	Inclination of maxillary first molar	
L1-MP (°)	Angle of mandibular incisor relative to mandibular plane	
Molar Relationship (mm)	Distal of U6 and L6 in relation to occlusal plane	
Overjet (mm) Anteroposterior distance from U1 tip to L1 tip		
Overbite (mm)	Vertical distance from U1 tip to L1 tip	

Cephalometric Maxillary Sagittal Skeletal Measurements

SNA Angle (°)	Sella-Nasion to A point	-
Point A to nasion perp (mm)	A point in relation to Nasion perpendicular	
Co-A (mm)	Maxillary length, Condylion to A point	=

Cephalometric Mandibular Sagittal Skeletal Measurements

SNB Angle (°)	Sella-Nasion to B point	
Pg to nasion perp, mm	Pogonion in relation to Nasion perpendicular	
Co-Gn, mm	Mandibular length, Condylion to Gonion	

Cephalometric Maxillomandibular Measurements

ANB (°)	Skeletal relationship, Angle from A point to Nasion to B point
Wits, mm	Jaw disharmony using A point and B point relative to occlusal plane
Max-Mand differential (mm)	Difference between Co-Gn and Co-A

IRB Version: 5/6/19

Cephalometric Vertical Skeletal Measurements

ANS-Me (mm)	Lower facial height, Anterior nasal spine to Menton
FH to mand plane (°)	Mandibular plane angle in relation to Frankfort horizontal
FH to occlusal plane (°)	Occlusal plane in relation to Frankfort horizontal
FH to mand plane (°)	Mandibular plane angle in relation to Sella-Nasion
SN to occlusal plane (°)	Occlusal plane in relation to Sella-Nasion
Ar-Go-Me (°)	Gonial angle

- 12.3 List any instruments or measurement tools used to collect data (e.g. questionnaire, interview guide, validated instrument, data collection form).
 - Include copies of these documents with your submission.

Response:

All de-identified measurements will be placed in a microsoft excel document (a sample of this document will be submitted with this form).

12.4 Describe any source records that will be used to collect data about subjects (e.g. school records, electronic medical records).

Response:

Axium medical records will be accessed in order to obtain patient age to determine if he or she is eligible for our study and to calculate total treatment duration (in months). Imaging records (Radiographs, Intraoral and Extraoral Photographs, 3D Intraoral Scans) and Clinical evaluation will be used to collect data.

12.5 Indicate whether or not **individual** subject results, such as results of investigational diagnostic tests, genetic tests, or incidental findings will be shared with subjects or others (e.g., the subject's primary care physician) and if so, describe how these will be shared.

Response:

If there are any findings relating to the subject's dental health will be shared with the subject and guardian and will also be notified to their primary care provider when necessary. If any anecdotal findings arise, they will be mentioned to the subject and guardians as well.

12.6 Indicate whether or not **study** results will be shared with subjects or others, and if so, describe how these will be shared.

Response:

If the subjects wish to know the results of the study, they will be notified in person once all data results have been calculated and analyzed.

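### U6-Y and L6-Y changes are listed as dental outcomes but measure tooth plus jaw displacement, and no listed measure isolates first-molar movement in mm within its own jaw.

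*Protocol*

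**What the plan says.** All references are to the Protocol.

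- **Axes (12.2, dentoalveolar table).** The X-axis is "SN minus 7 degrees". The Y-axis is "Perpendicular line to the X-axis drawn through the S point".
- **Measures on those axes (same table).** U6-Y is "Linear distance of the maxillary first molar to the Y plane", L6-Y is "Linear distance of the mandibular first molar to the Y plane" and L1-Y is "Linear distance of the mandibular central incisor to the Y plane".
- **How change is formed (12.1, Superimposition & Data Analysis).** "Initial cephalometric measurement (T0) will be subtracted from final cephalometric measurements (T1) for each value".
- **Cephalometric superimposition (12.1).** "Superimpositions will be constructed using T0 and T1 lateral cephalometric tracings". No registration structure is named, and no entry in the 12.2 cephalometric tables is derived from a superimposition. The reliability check repeats the superimpositions together with the landmarking and measurements.
- **Digital models (5.1, 12.1, 12.2).** The position of the maxillary molar and canine is recorded from the models at T0 and T1. The stated use of the maxillary model superimposition is molar and canine rotation.
- **Hypotheses (2.2).** Skeletal change (hypothesis 2) and dental change (hypothesis 3) are tested separately.
- **Population and timing (8.1, 12.1, 13.2).** Patients are growing, aged about 12 to 17 years 11 months. T1 is the visit at which the patient's own correction is complete, expected at 5 months give or take 1 month.

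**The concern.** A distance to a line through S changes when the tooth moves in its jaw, when the jaw moves relative to the cranial base, or when S or N is placed differently on the second tracing. The table files these distances as dentoalveolar, so the results would naturally be reported under hypothesis 3 as dental change.

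Forward jaw displacement makes upper molar distalization look smaller than it was and lower molar mesial movement look larger. Section 4.1 cites mesial movement of the lower molar as a reported side effect of the CMA, and one study with restricted maxillary growth at point A, so both components matter in this setting.

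The T0-T1 interval is also tied to the primary outcome, treatment time. If one appliance works faster, its patients have less time to grow before T1, and the Y-axis changes can differ between arms without any difference in tooth movement.

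**Working it through.** **1. What each listed measure can isolate.** From the tables in 12.2:

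| Tooth | On the S-N based axis | Other listed measures | Movement in mm within its own jaw? |
|---|---|---|---|
| U6 | U6-Y | U6-PP (an angle); molar relationship (U6 against L6) | No |
| L6 | L6-Y | molar relationship (U6 against L6) | No |
| L1 | L1-Y | L1-NB (mm, degrees), L1-APo (mm), IMPA, L1-MP | Jaw-referenced alternatives exist |

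Molar relationship is a difference between two teeth, so it cannot say which tooth or jaw moved. For the lower incisor, L1-NB is "Linear distance of the mandibular incisor to a vertical line drawn through Nasion and Point B" and does not use the S-based axis. The gap is therefore at the two first molars.

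**2. The plan's own figure.** Section 19.2 gives 80% power, alpha 0.05 and a standardized effect of 1.02366 for treatment time. A two-sided two-sample t-test (noncentral t) gives n = 16.0 per group and power 0.800 at 16 per group, so the figure reproduces. The protocol gives no SD and makes no power claim for any cephalometric measure; 1.02 SD is used below only as a yardstick.

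**3. Jaw displacement.** Assumption, not in the protocol: forward displacement g of 0.5 to 3 mm per year.

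- Added to each arm's mean change over 4 to 6 months: g × months / 12. Low end 0.5 × 4/12 = 0.17 mm; high end 3 × 6/12 = 1.5 mm.
- Shift between arms if mean durations differ by 1 to 2 months: low end 0.5 × 1/12 = 0.04 mm; high end 3 × 2/12 = 0.5 mm.
- Shift between arms if durations and jaw effects are equal: zero in expectation.

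**4. Axis error, if the axes are redrawn on each film.** Assumptions, none in the protocol: S-N 70 mm; molar 70 mm below S; an N error that is purely vertical, with SD e per film and independent between films; SD of true molar movement 1.5 mm (variance 2.25 mm²).

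- Shift at the tooth per film = depth × e / SN = 70 × e / 70 = e mm.
- Variance added to the two-film difference = 2e².
- Observed effect = 1.02366 × √(2.25 / (2.25 + 2e²)).

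| e (mm) | Axis tilt (degrees) | Total variance (mm²) | Observed effect (SD) | Power at 16 per arm |
|---|---|---|---|---|
| 0 | 0 | 2.25 | 1.02 | 80% |
| 0.5 | 0.41 | 2.75 | 0.93 | 72% |
| 0.75 | 0.61 | 3.375 | 0.84 | 63% |
| 1.0 | 0.82 | 4.25 | 0.74 | 53% |

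The first row is an error-free comparator. Superimposition carries registration and landmark error of its own, so the recoverable loss is smaller than the table suggests.

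**The case against.** The case for leaving the plan alone has several sound parts.

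- **Randomization.** Jaw displacement common to both arms cancels in expectation. A reader might infer that hypothesis 3 would be falsely rejected because of axis error. That does not follow: one operator traces both arms by one method, and random error unrelated to arm costs precision without raising false rejections.
- **Superimpositions.** A reader might infer that none of the planned superimpositions is used. That is true only of the cephalometric ones; the maxillary model superimpositions feed the rotation outcome.
- **Other measures.** The lower incisor has jaw-referenced measures. SNA, SNB, ANB and the nasion-perpendicular distances come from the same films, so jaw change is at least reported alongside. Maxillary molar position is also recorded from the models, though its stated use is rotation, and nothing equivalent exists for L6.
- **Tracing detail.** The text does not say that the axes are redrawn at T1. The reliability check treats superimposition as part of the measuring routine, so the T0 axes might be transferred. The axis-error calculation is therefore conditional.
- **Standing.** These are secondary outcomes in a pilot trial, and the choice of reference method is partly a matter of preference.

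All of this limits the consequences. It does not change what U6-Y and L6-Y measure, and it does not supply the missing molar measure. The definitions are fixed in the protocol itself, in the section meant to allow replication.

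**Conclusion.** The point holds in a limited form. As defined, U6-Y, L6-Y and L1-Y changes are total displacement, and for the first molars nothing in the list separates tooth from jaw in mm. Hypothesis 3 therefore cannot be answered for the molars as dental change distinct from hypothesis 2.

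Bias between arms needs a difference in T0-T1 duration or in jaw effect by appliance. For duration it is illustratively 0.04 to 0.5 mm, on assumed displacement of 0.5 to 3 mm per year and a 1 to 2 month difference. Otherwise the cost is in interpreting the within-arm changes and in precision. The precision loss, from 1.02 to about 0.93 to 0.74 SD, applies only if the axes are redrawn and rests wholly on the stated assumptions. Its lower end should not be read as the expected loss. This is an inexpensive improvement to secondary outcomes and does not affect the primary comparison.

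**What to change.** In 12.1:

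1. Name the structures on which the cephalometric superimpositions are registered.
2. Carry the T0 X- and Y-axes to the T1 tracing through the cranial-base superimposition.
3. Take U6 and L6 horizontal movement for hypothesis 3 from maxillary and mandibular regional superimpositions of the same tracings, and add these two measures to the table in 12.2.
4. Report U6-Y, L6-Y and L1-Y as total (skeletal plus dental) displacement.

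**Cost.** No new films and no new operator; a little more tracing time. Regional registration brings some error of its own, which the planned repeat measurements can quantify if they include the new measures, although that check covers only 5 cephalograms. No change in sample size follows, because the protocol gives no SD for any cephalometric measure.
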